## **7.0 TRIAL PROCEDURES**

### **7.1 Trial Procedures**

The Trial Flow Chart - Section 6.0 summarizes the trial procedures to be performed at each visit. Individual trial procedures are described in detail below. It may be necessary to perform these procedures at unscheduled time points if deemed clinically necessary by the investigator.

Furthermore, additional evaluations/testing may be deemed necessary by the sponsor for reasons related to participant safety. In some cases, such evaluation/testing may be potentially sensitive in nature (e.g., HIV, Hepatitis C, etc.), and thus local regulations may require that additional informed consent be obtained from the participant. In these cases, such evaluations/testing will be performed in accordance with those regulations.

#### **7.1.1 Administrative Procedures**

##### **7.1.1.1 Informed Consent**

The investigator must obtain documented consent from each potential participant prior to participating in the clinical trial.

##### **7.1.1.1.1 General Informed Consent**

Consent (both pre-screening and screening consent forms) must be documented by the participant's dated signature or by the participant's legally acceptable representative's dated signature on a consent form along with the dated signature of the person conducting the consent discussion.

A copy of the signed and dated consent form should be given to the participant before participation in the trial.

The initial informed consent form, any subsequent revised written informed consent form and any written information provided to the participant must receive the IRB/ERC's approval/favorable opinion in advance of use. The participant or his/her legally acceptable representative should be informed in a timely manner if new information becomes available that may be relevant to the participant's willingness to continue participation in the trial. The communication of this information will be provided and documented via a revised consent form or addendum to the original consent form that captures the participant's dated signature or by the participant's legally acceptable representative's dated signature.

Specifics about a trial and the trial population will be added to the consent form template at the protocol level.

The informed consent will adhere to IRB/ERC requirements, applicable laws and regulations and Sponsor requirements.

#### **7.1.1.2 Inclusion/Exclusion Criteria**

All inclusion and exclusion criteria will be reviewed by the investigator or qualified designee to ensure that the participant qualifies for the trial.

#### **7.1.1.3 Medical History**

A medical history will be obtained by the investigator or qualified designee. Medical history will include all active conditions, and any condition diagnosed within the prior 10 years that are considered to be clinically significant by the investigator. Details regarding the disease for which the participant has enrolled in this study will be recorded separately and not listed as medical history.

#### **7.1.1.4 Prior and Concomitant Medications Review**

##### **7.1.1.4.1 Prior Medications**

The investigator or qualified designee will review prior medication use, including any protocol-specified washout requirement, and record prior medication taken by the participant within 28 days before starting the trial. Treatment for the disease for which the participant has enrolled in this study will be recorded separately and not listed as a prior medication.

##### **7.1.1.4.2 Concomitant Medications**

The investigator or qualified designee will record medication, if any, taken by the participant during the trial. All medications related to reportable SAEs and ECIs should be recorded as defined in Section 7.2.

#### **7.1.1.5 Disease Details and Treatments**

##### **7.1.1.5.1 Disease Details**

The investigator or qualified designee will obtain prior and current details regarding disease status.

##### **7.1.1.5.2 Prior Treatment Details**

The investigator or qualified designee will review all prior cancer treatments, including systemic treatments, radiation and surgeries.

##### **7.1.1.5.3 Subsequent Anti-Cancer Therapy Status**

The investigator or qualified designee will review all new anti-neoplastic therapy initiated after the last dose of trial treatment. If a participant initiates a new anti-cancer therapy within 30 days after the last dose of trial treatment, the 30 day Safety Follow-up visit must occur before the first dose of the new therapy. Once new anti-cancer therapy has been initiated, the participant will move into survival follow-up.

#### **7.1.1.6 Assignment of Screening Number**

All consented subjects will be assigned a unique screening number that will be used to identify the subject for all procedures that occur prior to treatment allocation. Each subject will be assigned only one screening number. Screening numbers must not be re-used for different subjects. Any subject who is screened multiple times will retain the original screening number assigned at the initial screening visit.

#### **7.1.1.7 Assignment of Randomization Number**

All eligible subjects will be allocated, by non-random assignment, to trial treatment and will receive a unique treatment allocation number. The allocation number identifies the subject for all procedures. This unique number is termed an allocation number throughout the protocol for operational purposes. Once an allocation number is assigned to a subject, it can never be re-assigned to another subject. A subject cannot be assigned more than 1 allocation number.

#### **7.1.1.8 Trial Compliance (Medication/Diet/Activity/Other)**

Interruptions from the protocol specified treatment plan for > 12 weeks between doses of pembrolizumab due to toxicity require consultation between the investigator and the sponsor and written documentation of the collaborative decision on subject management.

Administration of pembrolizumab will be witnessed by the investigator and/or trial staff. The total volume of pembrolizumab infused will be compared to the total volume prepared to determine compliance with each dose administered.

The instructions for preparing and administering pembrolizumab will be provided in the Pharmacy Manual.

### **7.1.2 Clinical Procedures/Assessments**

#### **7.1.2.1 Adverse Event (AE) Monitoring**

The investigator or qualified designee will assess each participant to evaluate for potential new or worsening AEs as specified in the Trial Flow Chart and more frequently if clinically indicated. Adverse experiences will be graded and recorded throughout the study and during the follow-up period according to NCI CTCAE Version 4.0 (see Appendix 2). Toxicities will be characterized in terms regarding seriousness, causality, toxicity grading, and action taken with regard to trial treatment.

Please refer to section 7.2 for detailed information regarding the assessment and recording of AEs.

#### **7.1.2.2 Full Physical Exam**

The investigator or qualified designee will perform a complete physical exam during the screening period. Clinically significant abnormal findings should be recorded as medical history. A full physical exam should be performed during screening,

### **7.1.2.3 Directed Physical Exam**

For cycles that do not require a full physical exam per the Trial Flow Chart, the investigator or qualified designee will perform a directed physical exam as clinically indicated prior to trial treatment administration.

### **7.1.2.4 Vital Signs**

The investigator or qualified designee will take vital signs at screening, prior to the administration of each dose of trial treatment and at treatment discontinuation as specified in the Trial Flow Chart (Section 6.0). Vital signs should include temperature, pulse, respiratory rate, weight and blood pressure. Height will be measured at screening only.

### **7.1.2.5 Eastern Cooperative Oncology Group (ECOG) Performance Scale**

The investigator or qualified designee will assess ECOG status (Appendix 2) at screening, prior to the administration of each dose of trial treatment, and at discontinuation of trial treatment as specified in the Trial Flow Chart.

### **7.1.2.6 Tumor Imaging and Assessment of Disease**

Tumor imaging will include positron emission tomography (PET) with combined diagnostic quality computed tomography (CT) scans throughout the study. For the abdomen and pelvis, contrast-enhanced magnetic resonance imaging (MRI) may be used when CT with iodinated contrast is contraindicated, or when local practice mandates it. The same imaging technique regarding modality, ideally the same scanner, and the use of contrast should be used in a participant throughout the study to optimize the reproducibility of the assessment of existing and new tumor burden and improve the accuracy of the assessment of response or progression based on imaging.

Local reading (investigator assessment with site radiology reading) will be used in determining subject eligibility and response. Response to pembrolizumab will be evaluated using LYRIC response criteria (1). The sponsor will also receive radiologic images if the primary efficacy endpoint of the trial is met in order to retrospectively confirm subject eligibility and treatment response through a contracted centralized vendor.

#### **7.1.2.6.1 Initial Tumor Imaging**

Initial tumor imaging performed at screening must be conducted within 28 days prior to the date of treatment allocation, and consist of both PET and diagnostic CT scans of the neck, chest, abdomen and pelvis. The site study team must review screening images to confirm the participant has measurable disease as defined in the inclusion criteria. The baseline imaging scans must also be submitted to the central imaging vendor for a retrospective analysis of this eligibility criterion if the primary efficacy objective is met.

Tumor imaging performed as part of routine clinical management is acceptable for use as screening tumor imaging if they are of diagnostic quality and performed within 28 days prior to the date of allocation and can be assessed by the central imaging vendor.

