##### **5.1.1 Participant Inclusion Criteria**

Participants are eligible to be included in the study if all of the following criteria apply:

1. Male/female participants who are at least 18 years of age on the day of signing informed consent with a histologically confirmed diagnosis of DLBCL will be enrolled in this study.

*Note: Patients with high-grade B cell lymphomas not otherwise specified and those with MYC and BCL2 translocations (double hit lymphoma) are eligible, as are patients with transformed indolent lymphoma, so long as PD-L1 gene alterations are present.*

2. A male participant must agree to use a contraception as detailed in Appendix 4 of this protocol during the treatment period, and for at least 120 days after the last dose of study treatment and refrain from donating sperm during this period.
3. A female participant is eligible to participate if she is not pregnant (see Appendix 4), not breastfeeding, and at least one of the following conditions applies:
  - a.) Not a woman of childbearing potential (WOCBP) as defined in Appendix 4
  - b.) A WOCBP who agrees to follow the contraceptive guidance in Appendix 4 during the treatment period and for at least 120 days after the last dose of study treatment.
  - c.) patient must have negative pregnancy test within 72 hours of beginning treatment if WOCBP
4. The participant (or legally acceptable representative if applicable) provides written informed consent for the trial.

5. Have measurable disease, defined as at least one lesion that can be accurately measured in at least two dimensions by CT scan. Minimum measurement must be >15 mm in the longest diameter by >10 mm in the short axis. Lesions situated in a previously irradiated area are considered measurable if radiographic progression has been demonstrated in such lesions.

6. Participants must have available archived biopsy material (ideally to be performed shortly before enrollment at the time of most recent relapse) for *PD-L1* FISH and correlative studies. Formalin-fixed, paraffin embedded (FFPE) tissue blocks are preferred to slides.

*Note: If submitting unstained cut slides, newly cut slides should be submitted within 14 days from the date slides are cut if possible.*

7. There is evidence of a *PD-L1* gene alteration within lymphoma cells as assessed by FISH. See Appendix 1 for detailed description of what constitutes the presence of a *PD-L1* gene alteration.

8. Participants must have received either:

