8. Is currently participating in or has participated in a study of an investigational agent or has used an investigational device within 4 weeks prior to the first dose of study treatment.
9. Has a diagnosis of immunodeficiency or is receiving chronic systemic steroid therapy (in dosing exceeding 10 mg daily of prednisone equivalent) or any other form of immunosuppressive therapy within 7 days prior to the first dose of study drug. Short courses of corticosteroids will be allowed for palliation of symptoms related to lymphoma, but must be discontinued within 7 days prior to the first dose of study drug.
10. Subjects having received prior allogeneic stem cell transplant, must be at least 5 years removed from the date of their transplant. The also must have no history of severe (grade 3-4) acute GVHD, and/or current > grade 1 acute GHVD. Subjects must not have active chronic GVHD that requires active immune suppression or more than 10 mg of prednisone/day or equivalent.
11. Has a history of a solid organ transplant.
12. Has a known additional malignancy that is progressing or has required active treatment within the past 3 years. Note: Participants with basal cell carcinoma of the skin, squamous cell carcinoma of the skin, or carcinoma in situ (e.g. breast carcinoma, cervical cancer in situ) that have undergone potentially curative therapy are not excluded
13. Has severe hypersensitivity ( $\geq$ Grade 3) to pembrolizumab and/or any of its excipients.
14. Has active autoimmune disease that has required systemic treatment in the past 2 years (i.e. with use of disease modifying agents, corticosteroids or immunosuppressive drugs).

Replacement therapy (eg., thyroxine, insulin, or physiologic corticosteroid replacement therapy for adrenal or pituitary insufficiency, etc.) is not considered a form of systemic treatment.

15. Has a history of (non-infectious) pneumonitis that required steroids or has current pneumonitis.
16. Has an active infection requiring systemic therapy.
17. Has a known history of Human Immunodeficiency Virus (HIV) infection.
18. Has a known history of Hepatitis B (defined as Hepatitis B surface antigen [HBsAg] reactive) or known active Hepatitis C virus (defined as detection of HCV RNA) infection.
19. Has a known history of active TB (Bacillus Tuberculosis).

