## 5.2 Trial Treatments

The treatment to be used in this trial is outlined below in Table 2

Table 2. Trial Treatment

Drug	Dose/Potency	Dose Frequency	Route of Administration	Regimen/Treatment Period	Use
Pembrolizumab	200 mg	Q3W	IV infusion	Day 1 of each 3 week cycle	Experimental

Trial treatment should begin on or as close as possible to the day of allocation.

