#### **5.5.2 Prohibited Concomitant Medications**

Participants are prohibited from receiving the following therapies during the screening and treatment phase of this trial:

- Anti-neoplastic biological therapy
- Immunotherapy not specified in this protocol
- Chemotherapy
- Investigational agents other than pembrolizumab
- Radiation therapy

- Note: Radiation therapy to a symptomatic solitary lesion may be allowed at the investigator's discretion, provided that study treatment is initiated at least 7 days after completion of all palliative radiation..
- Live vaccines within 30 days prior to the first dose of study treatment and while participating in the study. Examples of live vaccines include, but are not limited to, the following: measles, mumps, rubella, varicella/zoster, yellow fever, rabies, BCG, and typhoid vaccine. Seasonal influenza vaccines for injection are generally killed virus vaccines and are allowed; however, intranasal influenza vaccines (eg, FluMist®) are live attenuated vaccines and are not allowed.
- Systemic glucocorticoids for any purpose other than to modulate symptoms from an immune-related adverse event, or the use of palliative glucocorticoids during the screening phase of the study (steroids however must be discontinued within 7 days of the first dose of pembrolizumab treatment). The use of physiologic doses of corticosteroids may be approved after consultation with the sponsor.

Participants who, in the assessment by the investigator, require the use of any of the aforementioned treatments for clinical management should be removed from the study. All treatments that the investigator considers necessary for a participant's welfare may be administered at the discretion of the investigator in keeping with the standards of medical care.

Medications or vaccinations specifically prohibited in the exclusion criteria are not allowed during the ongoing study. If there is a clinical indication for any medication or vaccination specifically prohibited during the study, discontinuation from study therapy or vaccination may be required. The final decision on any supportive therapy or vaccination rests with the investigator and/or the participant's primary physician. However, the decision to continue the participant on study treatment requires the mutual agreement of the investigator, the Sponsor and the participant.

There are no prohibited therapies during the Post-Treatment Follow-up Phase.

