## **5.8 Criteria for Early Trial Termination**

Early trial termination will be the result of the criteria specified below:

1. Quality or quantity of data recording is inaccurate or incomplete
2. Poor adherence to protocol and regulatory requirements
3. Incidence or severity of adverse drug reaction in this or other studies indicates a potential health hazard to participants
4. Plans to modify or discontinue the development of the study drug
5. The ORR does not meet stated hypothesis upon completion of the first phase of the study (< 3/13 responders)

In the event that Merck decides to no longer supply study drug, ample notification will be provided so that appropriate adjustments to participant treatment can be made.

[illegible]

Trial Period:	Screening Phase		Treatment Cycles a								End of Treatment	Post-Treatment		
Treatment Cycle/Title:	Pre-screening (Visit 1)	Main Study Screening (Visit 2)	1	2	3	4	To be repeated beyond 8 cycles				Discon	Safety Follow-up	Follow Up Visits	Survival Follow-Up
							5	6	7	8				
Scheduling Window (Days):	-28 to -11	-10 to -1		± 3	± 3	± 3	± 3	± 3	± 3	± 3	At time of Discon	30 days post discon	Every 12 weeks post discon	Every 12 weeks
LDH		X	X	X	X	X	X	X	X	X	X			
Urinalysis		X					X				X	X		
TSH		X			X		X				X	X		
Efficacy Measurements														
Tumor Imaging and bone marrow exam b		X b				X				X	X			
Tumor Biopsies/Archival Tissue Collection/Correlative Studies Blood														
PD-L1 FISH Assessment	X													
Archival or Newly Obtained Tissue Collection		X									X c			
Correlative Studies Blood Collection		X		X			X				X			
Baseline Stool Collection		X												

a For women of reproductive potential, a urine pregnancy test will be performed within 72 hours prior to the first dose of trial treatment. If urine pregnancy results cannot be confirmed as negative, a serum pregnancy test will be required (performed by the local study site laboratory).

bTumor imaging to consist of a PET scan and diagnostic CT scans of neck, chest, abdomen, and pelvis. Scans performed within 28 days of treatment allocation will be allowable. Bone marrow biopsy to also be performed at times of tumor imaging for patients with baseline involvement (this does not need to be performed for patients with clear progression on diagnostic imaging, and does not need to be repeated for patients with documented bone marrow clearance unless otherwise clinically indicated).

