Lugano	PET-CT, score 1, 2, or 3* with or without a residual mass on 5PS† OR on CT, target nodes/nodal masses must regress to ≤1.5 cm in LDi	PET-CT score 4 or 5 with reduced uptake compared with baseline and residual mass(es) of any size. OR On CT ≥50% decrease in SPD of up to 6 target measurable nodes and extranodal sites	PET-CT score 4 or 5 with an increase in intensity of uptake from baseline and/or new FDG-avid foci consistent with lymphoma at interim or end-of-treatment assessment. OR On CT, an individual node/lesion must be abnormal with: LDi >1.5 cm and increase by ≥50% from PPD nadir and an increase in LDi or SDi from nadir 0.5 cm for lesions ≤2 cm 1.0 cm for lesions >2 cm  In the setting of splenomegaly, the splenic length must increase by >50% of the extent of its prior increase beyond baseline (eg, a 15-cm spleen must increase to >16 cm). If no prior splenomegaly, must increase by ≥2 cm from baseline. New or recurrent splenomegaly New or clear progression of preexisting nonmeasured lesions Regrowth of previously resolved lesions A new node >1.5 cm in any axis or a new extranodal site >1.0 cm in any axis; if <1.0 cm in any axis, its presence must be unequivocal and must be attributable to lymphoma Assessable disease of any size unequivocally attributable to lymphoma AND/OR new or recurrent involvement of the bone marrow
LYRIC	Same as Lugano	Same as Lugano	As with Lugano with the following exceptions: IR IR(1): ≥50% increase in SPD in first 12 weeks IR(2): <50% increase in SPD with a. New lesion(s), or b. ≥50% increase in PPD of a lesion or set of lesions at any time during treatment IR(3): Increase in FDG uptake without a concomitant increase in lesion size meeting criteria for PD

IR, immune response; LDi, longest diameter; PPD, product of the perpendicular diameters; SDi, short diameter; 5PS, 5-point scale.

\*A score of 3 in many patients indicates a good prognosis with standard treatment, especially if at the time of an interim scan. However, in trials involving PET where de-escalation is investigated, it may be preferable to consider a score of 3 as inadequate response (to avoid undertreatment).

†PET 5PS: 1, no uptake above background; 2, uptake ≤ mediastinum; 3, uptake > mediastinum but ≤ liver; 4, uptake greater than liver; 5, uptake markedly higher than liver (2-3 times SUVmax in normal liver) and/or new lesions; X, new areas of uptake unlikely to be related to lymphoma.

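### A lesion irradiated after the baseline PET-CT can still be scored against that scan and count toward the single-arm response rate

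*Combined protocol and SAP*

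**What the plan says.** **Baseline scan.** Section 7.1.2.6.1: "Initial tumor imaging performed at screening must be conducted within 28 days prior to the date of treatment allocation". Routine-care scans are accepted in the same window, and Section 7.1.5.1 agrees. The flow chart (Section 6.0) places main screening at days -10 to -1, but footnote b widens this for imaging: "Scans performed within 28 days of treatment allocation will be allowable". The limit runs to allocation, not to dose 1. Section 5.2 sets no maximum gap between the two: "Trial treatment should begin on or as close as possible to the day of allocation".

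**Radiotherapy.** Section 5.5.2 covers the screening and treatment phase. It prohibits radiation, with an exception at the investigator's discretion for a symptomatic solitary lesion, "provided that study treatment is initiated at least 7 days after completion of all palliative radiation". Exclusion 4 (Section 5.1.2) sets the matching one-week limit.

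**Irradiated lesions.** The only rule is in inclusion criterion 5 (Section 5.1.1), which defines measurable disease: "Lesions situated in a previously irradiated area are considered measurable if radiographic progression has been demonstrated in such lesions". One measurable lesion is enough for entry.

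**Response.** The primary endpoint (Section 8.2.3.1) is a LYRIC objective response at any time, judged by the investigator. In Appendix 5, LYRIC takes CR and PR from Lugano. The PET limb of PR is "PET-CT score 4 or 5 with reduced uptake compared with baseline", with no numerical threshold. The first on-study scan is at 12 weeks ± 7 days (Section 7.1.2.6.2).

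**The concern.** Response is change from baseline, so the baseline image should show the disease as it stood when pembrolizumab began. Here a permitted local treatment with anti-tumour effect can fall between the two. A patient could be scanned on day -27, have a painful mass irradiated from day -20 to day -10, start pembrolizumab on day 0, and be compared at week 12 with the day -27 scan. Every step follows the plan, and a smaller or less avid mass could be recorded as a response to the drug.

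The trial has one arm and a fixed 15% benchmark, so no concurrent control carries the same effect. Where radiotherapy changes a reading in this way, it adds a responder. That favours passing stage 1 and declaring the biomarker strategy effective.

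**Working it through.** **1. Width of the gap.** Scan limit 28 days (7.1.2.6.1); radiotherapy must end 7 days before dose 1 (5.5.2, exclusion 4).
- Radiotherapy: 28 − 7 = 21 days after the earliest allowed scan, plus any delay from allocation to dose 1.
- Had the flow-chart column (day -10 at the earliest) applied to imaging: 10 − 7 = 3 days.
- Chemotherapy, antibodies and targeted drugs (exclusion 3, four weeks): 28 − 28 = about 0 days.

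The 28-day window is thus nearly matched by the washout for systemic drugs, but not for radiotherapy.

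**2. Is the gap closed elsewhere?** No passage orders the scan after radiotherapy, asks for a repeat scan, removes a lesion irradiated after the scan from response scoring, or gives an analysis rule for such patients.

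**3. The plan's own design figure.** Section 8.1.3: p0 = 0.15, p1 = 0.40, 13 then 29 patients, continue at ≥3/13, success at ≥8/29. With b(n,x,p) the binomial probability,

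P(success | p) = Σ over x = 3…13 of b(13,x,p) × P[Bin(16,p) ≥ 8 − x].

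- p = 0.15: 0.0500. p = 0.40: 0.907.
- P(early stop | 0.15) = 0.692; expected N = 13 + 0.308 × 16 = 17.9.
- A grid search returns this same design as optimal. The stated 5% and 90% are met, and the type I error has no room to spare.

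**4. One spurious responder.** Assume one patient is certain to be scored a responder because of radiotherapy, and all others have a true ORR of 15%.
- In stage 1: Σ over x = 2…12 of b(12,x,0.15) × P[Bin(16,0.15) ≥ 7 − x] = 0.107.
- In stage 2: Σ over x = 3…13 of b(13,x,0.15) × P[Bin(15,0.15) ≥ 7 − x] = 0.092.
- Two such patients: 0.152 (both in stage 2), 0.189 (one in each), 0.206 (both in stage 1).

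**5. The same as a rate.** Let f be the share of patients irradiated after the scan, and q the chance that a pembrolizumab non-responder among them reads as a response. Apparent ORR = 0.15 + 0.85 × f × q. The documents give neither f nor q; the values below are assumptions.

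| f | q | Apparent ORR | Spurious per 29 (29 × 0.85 × f × q) | False-positive rate |
|---|---|---|---|---|
| 5% | 25% | 0.1606 | 0.31 | 0.070 |
| 10% | 25% | 0.1712 | 0.62 | 0.094 |
| 10% | 50% | 0.1925 | 1.23 | 0.157 |

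**The case against.** **Existing safeguards.** Exclusion 20 lets the investigator exclude a patient whose therapy might confound the results, and exclusion 23 removes those needing immediate cytoreduction. If criterion 5 is judged at allocation, a lesion irradiated after the scan already lies in an irradiated field without shown progression. A patient with only that lesion would then be ineligible, which removes the worst case. If the endpoint is met, central review rechecks eligibility and response (Section 7.1.2.6). These points stand as reasons why the problem should be infrequent. They do not close it: exclusion 20 is a matter of opinion, exclusion 23 is narrower than the palliation that 5.5.2 permits, criterion 5 does not say when it is judged and does not govern response scoring, and central review has no instruction on such lesions.

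**Other disease.** The exception covers a single lesion, and Appendix 5 treats growth, increased uptake or new lesions elsewhere as progression or an indeterminate response. In a patient with further disease, a false response needs that disease to stay quiet for about 12 weeks. This stands and limits the size.

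**Steroids.** A reader might infer the same bias from the steroid allowance in exclusion 9: "Short courses of corticosteroids will be allowed for palliation of symptoms related to lymphoma". The documents do not support that. The first response scan is at about week 12, and nothing in them suggests that a short course stopped around the start of treatment still affects it.

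**Direction.** A reader might also infer that the net comparison must favour pembrolizumab. That does not follow. In unirradiated patients, growth between an early scan and dose 1 makes response against that baseline harder. The documents also do not say whether the KEYNOTE-013 cohort had similar screening allowances.

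**Conclusion.** The gap is real for radiotherapy. Followed as written, the plan allows a lesion irradiated after the baseline scan to be scored against that scan and to count toward the primary endpoint. The design calculation itself is correct; the issue is attribution of response.

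The size is unknown and probably small. The figures of 0.092 and 0.107 hold only if exactly one patient is misread, and the table rests on assumed f and q. It would be wrong to conclude that the trial's type I error is 9% or more; the documents give no frequency from which to estimate it. What the figures show is that, with type I error already at 0.050, a single misattributed patient roughly doubles it. Severity is moderate: a cheap improvement, not a flaw that invalidates the design.

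**What to change.** Add to Section 7.1.2.6.1 and flow chart footnote b:
- A lesion irradiated after the baseline scan is not a target lesion and cannot by itself support CR or PR on CT or PET. It still counts for progression.
- Criterion 5 is applied at allocation, so the patient needs at least one other measurable lesion that was not irradiated after that scan.

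Note the rule beside Appendix 5 as a trial-specific addition to LYRIC, and give it to the central reader. It should be set before results are known.

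**Cost.** A short amendment with no extra scan. The sample size, the cut-offs, the type I error of 0.050 and the power of 0.907 are unchanged. A patient whose only measurable lesion was irradiated after the scan would not qualify; that is the patient whose response could not be interpreted. Requiring a new baseline scan after radiotherapy is less good: regression that continues after the new scan would still be credited to the drug, and an extra scan may be needed.

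Separately, the timing of steroid discontinuation in exclusion 9 and Section 5.5.2 can be read as at least 7 days before dose 1 or as some time in the last 7 days. The two passages should be clarified and reconciled.
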